10.9.3 Case Processing and Submission to Competent Authorities

As the study is retrospective, all AEs collected during the study should have been reported to the competent authorities at time of occurrence. AEs collected during this study will not be submitted to the competent authorities as this would result in double reporting. However, all AESIs collected for the study will be recorded in the study database and summarized in the study report.

The investigators are responsible for maintaining compliance with any applicable site-specific requirements related to the reporting of SAEs or other safety information to the local IEC that approved the study.

11 DATA SOURCES

This is a retrospective, observational study, and patient data collected from the sites will be extracted from medical charts.

12 DATA MANAGEMENT

Electronic data collection will be performed using eCRFs. Site personnel will enter data into the EDC system according to the schedule of assessments and according to instructions from the Sponsor and/or designee. Only authorized personnel will have access to the EDC system. Selected eyes will be identified by an identification number assigned when they are selected for the study. For patients implanted bilaterally, both eyes can be entered into the study database if they both eyes meet eligibility criteria. In that case, each eye will be included in the study database with a unique identifier, and eyes will be paired in the EDC. Data will be anonymized and once entered in the system, investigators and study personnel will not be able to identify patients.

Each investigator is responsible for ensuring that accurate data are entered into the EDC system in a timely manner. Specific processes used to manage the data throughout the study will be documented in the Data Management Plan. Briefly, on-line logic checks will be built into the system, so that missing or illogical data are not submitted. In the event that inconsistent data persist, no queries will be issued as investigators will not be able to connect the patient with his/her eye identification number. Consequently, all data entered into the eCRF should be reviewed by the principal investigator. The principal investigator will be responsible for endorsing data within the eCRF. This approval method will include applying an electronic signature, a uniquely assigned user name, and a password that together will represent a traditional handwritten signature.

Medical history and AEs will be coded using Medical Dictionary for Regulatory Activities (MedDRA, the most recent version); coding will be done at the Lower Level Term. IOP lowering medications will be coded with the WHO Drug Dictionary.

A final validation of the database will be performed, and the database will be locked, before the statistical analysis is conducted.

13 QUALITY CONTROL

Designated study personnel will participate in a training program that will encourage consistency of process and procedures at the investigative site and ensure collection of high-quality data for this study. All sites will be trained on the protocol, study logistics, and the EDC. Retraining will be conducted as needed. Investigators will be reminded of the processes and importance of reporting AESI, SAEs, and other information.

Quality controls performed during statistical analyses will be described in the statistical analysis plan (SAP).

Secure electronic archive will be maintained and will include but will not be limited to: final raw data, analysis datasets, programs and associated documentation. Access to the archive will be controlled and limited to authorized personnel only.

14 STATISTICAL METHODS

14.1 Sample Size

To answer study primary objective, this chart review study plans to accrue a minimum of 60 study eyes that have had at least 3 years of follow-up data without a SSI for glaucoma after the initial implant with XEN 45 Gel Stent.

Data from the Allergan study MS-001 demonstrated that the mean IOP reduction from baseline differed slightly among the 7 visits (see below) in the 24-month post-implant period. The absence of a clear waning-out trend suggests that the effect of XEN 45 Gel Stent implantation on IOP reduction may last to Month 36 and beyond. The minimum mean reduction (negative sign stands for reduction) in IOP among the visits was -5.6 (± 6.32) mmHg, which was observed at Month 3. This value was then taken as an initial estimate for the mean reduction projected for Month 36. The 95% confidence interval (CI) of the projected mean reduction afforded by a sample of 60 study eyes is -7.2 to -4.0 mmHg. That is, the half-length of the interval is 1.6 mmHg, which provides a reasonable precision for the estimate of the projected mean reduction in IOP.

Table 4 Result from the MS-001 Study

Visit	Number of study eyes	Mean (SD) change in IOP from medicated baseline (mmHg)
Month 1	167	-6.3 (6.41)
Month 3	167	-5.6 (6.32)
Month 6	168	-6.4 (4.92)
Month 9	134	-6.1 (5.68)
Month 12	161	-6.7 (5.41)
Month 18	149	-7.1 (5.10)
Month 24	149	-6.2 (4.94)

The MS-001 study enrolled 199 patients (218 study eyes). In this study, patients' discontinuation rate tended to be linear over the 2-year follow-up period, with an overall study discontinuation rate of approximately 20%. Using data from the MS-001 study, it could be assumed that 30% of the eyes selected for this study have less than 3 years of follow-up data. Taking into consideration that MS-001 study was a clinical trial and that patient retention rate is expected to be lower in a real-world setting, the study will aim to select 150 eyes to ensure obtaining a minimum of 60 eyes with at least 3 years of follow-up data.

14.2 Study Populations and Analyses

A formal SAP that will provide details of all analyses and presentation of study data will be approved prior to data analysis. Statistical analysis will be carried out using SAS software version 9.2 or later.

14.2.1 Study Populations and Analysis Methods

- Analysis Population: all eyes selected and meeting the selection criteria.
- Subgroups analyses will be conducted in eyes that did or did not undergo phacoemulsification. Additional subgroups may be further considered in the SAP.

Continuous variables will be described by their mean, standard deviation, median, upper and lower quartiles, extreme values (minimum and maximum) and the number of missing data.

Categorical variables will be described by the number and percentage of each response and the number of missing data.

Figures will be generated, when appropriate, to describe change in parameters over time.

Some of the data will only be collected if they occurred within study-defined time windows (see Section 7.2). Since all data within the defined time windows will be collected, more than one value could be available per time window for a given parameter. Rules to determine which value will be used for the analysis will be defined in the SAP.

14.2.2 Disposition and Patients' characteristics

Number and percentage of eyes in the Analysis Population and in subgroups will be described. Demographic characteristics will be summarized descriptively at a patient level.

14.2.3 Disease Progression

Ocular medical history, IOP lowering medications and needling procedures will be summarized descriptively. Visual field exam and BCVA will be summarized descriptively at baseline and for all time points of interest.

14.2.4 Primary Objective

Change in IOP from medicated baseline and change in the number of topical IOP-lowering medications compared to baseline will be summarized descriptively at Year 3 after XEN 45 Gel Stent implantation in eyes from the Analysis Population with at least 3 years of follow-up data and were not treated with Diamox on the day when decision was taken to implant XEN 45 Gel Stent.

14.2.5 Secondary Objectives

14.2.5.1 Change in IOP and Number of Topical IOP-Lowering Medications 4 Years after XEN 45 Gel Stent Implantation

Change in IOP from medicated baseline and change in the number of topical IOP-lowering medications compared to baseline will be summarized descriptively at Year 4 after XEN 45 Gel Stent implantation in eyes from the Analysis Population with at least 4 years of follow-up data and were not treated with Diamox on the day when decision was taken to implant XEN 45 Gel Stent.

14.2.5.2 Success over the Long Term of following implantation of the XEN 45 Gel Stent

Number and proportion of eyes achieving a 20% reduction in IOP from medicated baseline, and number and proportion of eyes with an IOP <18 mmHg, IOP <17 mmHg, ..., down to IOP <12 mmHg will be described at all time-points of interest in eyes from the Analysis Population that did not undergo SSI for glaucoma, did not have clinical hypotony, and were not treated with Diamox on the day when decision was taken to implant XEN 45 Gel Stent.

The number and proportion of eyes achieving qualified or complete success at 3 and 4 years after XEN 45 Gel Stent implantation will be summarized descriptively. Analyses will be conducted in the Analysis Population. Kaplan-Meier analyses will be conducted to analyze time from initial procedure to SSI for glaucoma.

14.2.5.3 Safety over the long term following implantation of the XEN 45 Gel Stent

Surgical complications and post-operative AESIs will be summarized descriptively using frequencies and percentages. Analyses will be performed in the Analysis Population.

14.3 Bias and Limitations of the Study

14.3.1 Sites

Sites will be selected to be representative of sites experienced with glaucoma management. Because the participating sites comprise a population of volunteers, a non-response selection bias is possible.

14.3.2 Patients

In order to limit bias in the selection of patients' eyes, each site will be asked to select in a chronological order all eyes that meet the selection criteria, regardless of demography or other considerations, based on date of XEN 45 Gel Stent implantation (see Section 9.2). Exception to the selection in a chronological order will be made for patients with both eyes meeting the selection criteria with both eyes included at the same time. All patients' eyes that had XEN 45 Gel Stent implanted and meeting the selection criteria, regardless of whether or not they will be selected for the study, will be recorded in an anonymized screening log collecting minimum non-identifying patient information (see Section 10.1). Characteristics of selected and non-selected patients' eyes will be compared to assess selection bias and reason for not being selected will be described (eye did not meet selection criteria, lack of time, quotas were met, site was unable to retrieve data missing from the chart from other locations etc.).

14.3.3 Information Bias

As the study is retrospective, the study will rely on data collected for another purpose (e.g. patient care). As a result, not all data to be collected in this study may be recorded in the medical charts, leading to a potential bias due to missing data.

Moreover, as data are anonymized, no queries will be issued to the sites in case of missing or incoherent data.

Finally, as this is a multicenter study conducted in different countries, the quality and quantity of medical information available from medical records will be variable. Medical records from some providers may not contain information for all encounters with the ophthalmologist. To limit this bias, it will be verified during the feasibility assessment that targeted sites have access to complete patient records, including patients' follow up after implantation. In case key data are missing from the charts at the site, site personnel will be asked to liaise with the patients' treating ophthalmologist to request data to be made available for investigators for data entry. Finally the methods used to estimate the data variables collected (e.g. visual field, best corrected visual acuity...) during the chart review process may be heterogeneous across sites. This could potentially result in greater variability in the study result.

Information bias can be minimized by the use of electronic data capture technology. In addition to minimize the burden on the investigators and the sites, electronic data capture technology will maximize the quality and relevance of the data using automated online controls (e.g., automated controls on value ranges, units, internal consistency, and missing key data).

15 ETHICAL CONDUCT OF THE STUDY

15.1 Ethics Statement

To ensure the quality and integrity of research, the study shall be conducted in compliance with the ethical principles arising from the Declaration of Helsinki revised in 2013 (World Medical Association, 2013), ISO-14155-2011 (ISO, 2011), the MEDDEV 2.12/2 rev2 (MEDDEV, 2012), European and National laws in terms of data protection and all current local regulations (2016/679, 2016).

15.2 Informed Consent

Due to the retrospective and anonymous nature of data collection for this study, signature of informed consent by patients is not required to extract data from the patient's chart. A waiver of consent will be requested from IECs.

15.3 Institutional Review Board / Independent Ethics Committee Approval

This study is non-interventional. As the study is based on a secondary use of data, it does not come under applicable laws and regulation on clinical trials

Submissions and/or notification to the appropriate IEC will be performed as required by local legislation in each country for this type of study.

Patients' personal data and investigator's personal data shall be treated in compliance with the European Regulation (EU 2016/679) on the protection of individuals with regard to the processing of personal data and all local applicable laws and regulations.

Data about investigators will be declared to applicable data protection authority and the investigators will be informed – within the framework of the site qualification questionnaire – of their right to access to, rectify or erase data, or their right to restrict or object to processing of the data, as well as the right to data portability.

Patient data will be anonymized, i.e. investigators will not be able to connect the patient with his/her identification number. The sponsor will be blinded to the patient information.

Submission(s) to competent data protection authorities will be performed as appropriate.

15.4 Adherence to the Protocol

The study must be conducted as described in the approved protocol. Any significant deviation from the protocol (i.e. jeopardizing patient safety) must be reported immediately to the Sponsor and IEC.

15.5 Protocol Amendment

Any amendment to the protocol will be created by the Sponsor, and subsequently submitted by the site to the IEC and appropriate regulatory authority for approval.

15.6 Retention of Patient Records

When the study is completed, the investigators must retain the essential documents for as long as needed to comply with regulatory guidelines and Sponsor requirements. The investigators will notify the Sponsor prior to moving or destroying any of the study documents.

The Sponsor will maintain the data collected (study database) for at least 5 years.

16 PLANS FOR DISSEMINATING AND COMMUNICATING STUDY REPORT

The Sponsor and/or designee will develop a final study report after the end of the study. Results will be posted on Clinical Trials.gov.

This study is intended for publication, even if terminated prematurely. Publication may include any or all of the following: posting of a synopsis online, abstract and/or presentation at a scientific conference, or publication of a full manuscript. . Authorship credit will follow the guidelines established by the International Committee of Medical Journals Editors (ICMJE, 2016) and, as such, should be based on the following criteria 1) substantial contributions to the conception or design of the work; or the acquisition, analysis, or interpretation of data for the work; 2) drafting the work or revising it critically for important intellectual content; 3) final approval of the version to be published and 4) agreement to be accountable for all aspects of the work in ensuring that questions related to the accuracy or integrity of any part of the work are appropriately investigated and resolved. All authors must meet all above criteria. Although publication planning may begin before conducting the study, final decisions on authorship and the order of authors' names will be made based on participation and actual contributions to the study and writing, as discussed above.

1.1. Background

The term “glaucoma” refers to a group of diseases that have in common a characteristic damage to the optic nerve with associated visual field loss. The goal in the treatment of glaucoma is to prevent further loss of functional vision and to avoid an adverse impact on the patient’s quality of life.¹ Currently, the only approach proven to be efficient in preserving visual function is lowering intra-ocular pressure (IOP)² as elevated IOP is recognised as the primary risk factor for glaucoma.

XEN 45 Gel Stent (Allergan Inc.) is an *ab interno* gelatin stent implanted via a clear corneal incision without conjunctival incision and is the only available filtering micro-invasive glaucoma surgery device that allows subconjunctival filtration. The XEN 45 Gel Stent is intended to reduce IOP in patients with primary open angle glaucoma where previous medical treatments have failed (XEN 45 Gel Stent directions for use). The performance and safety of XEN 45 Gel Stent has been previously demonstrated in a few clinical trials but the follow-up time has only been up to two years.

1.2. Study Rationale

XEN 45 Gel Stent performance and safety have been previously demonstrated in clinical trials designed for regulatory approval, and these studies only provide data for up to 2 years. This study will allow an assessment of the long-term performance and safety of the XEN 45 Gel Stent surgeries performed in Europe in typical clinical settings.

1.3. Study Objectives

1.3.1. Primary objective

The primary objective of this study is to assess the performance of XEN 45 Gel Stent over the long term as assessed by the change in IOP compared to medicated IOP at baseline and the change in the number of topical IOP-lowering medications compared to baseline, 3 years after implantation.

1.3.2. Secondary objective

The secondary objectives of this study are to:

- Assess the performance of XEN 45 Gel Stent over the long term as assessed by the change in IOP compared to medicated IOP at baseline and the change in the number of topical IOP-lowering medications compared to baseline, 4 years after implantation.
- Assess success over the long term following implantation of the XEN 45 Gel Stent as defined in Section 1.4.
- Assess safety over the long term following implantation of the XEN 45 Gel Stent.

1.4. Key Variable Definitions

Qualified success of implantation of the XEN 45 Gel Stent will be defined as $\geq 20\%$ reduction from medicated baseline with no Secondary Surgical Intervention (SSI) for glaucoma and no clinical hypotony while staying on the same number or fewer topical IOP-lowering medications than at baseline.

Complete success of implantation of the XEN 45 Gel Stent will be defined as $\geq 20\%$ reduction from medicated baseline with no SSI for glaucoma and no clinical hypotony while taking no topical IOP-lowering medications.

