10.7 Needling Procedures

Date of needling procedures performed on the bleb after XEN 45 Gel Stent implantation will be collected throughout the study period.

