10.8 Secondary Surgical Intervention

If a SSI for glaucoma was performed on the study eye during the study period, the nature and date of the SSI will be collected. SSIs for glaucoma include but are not limited to trabeculectomy, table shunt, second gel stent, i-Stent, GATT, ABiC, and transscleral cycloablative procedures.

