1.6. Study Design

This is a retrospective, non-interventional, observational, multi-centre, chart review study conducted in patients who underwent placement of the XEN 45 Gel Stent as a standalone procedure or in combination with phacoemulsification from 1 January 2014 to 1 October 2015.

For each eligible eye, all retrospective data available from baseline (i.e. day when decision was made to implant XEN 45 Gel Stent) until Last Visit (i.e. date of the last follow-up visit available prior to 1 October 2018 or date on which the patient had a SSI for glaucoma, whichever occurs first) are extracted from existing medical records into the electronic CRF (eCRF) in Dacima.

If both eyes from the same patient meet eligibility criteria, each eye is included in the study database with a unique identifier and eyes are paired in the electronic data capture system (EDC). See section 4 for how bilateral eyes included in the study are handled in the analyses.

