4.3. Disease progression

Ocular medical history will be summarised descriptively in the Safety Population overall and not by the time windows specified. Needling procedures will be summarized in the Safety Population by the time windows indicated in Section 4.1. Anti-metabolite/anti-fibrotic use will be described during the stent implantation, during conjunctiva bleb revision (if applicable), during needling procedures (if applicable), and also when used alone. Anti-metabolite/anti-fibrotic use during needling procedures will be determined based on the date of each anti-metabolite/anti-fibrotic use and date of the needling procedure; the same date assumes that the anti-metabolite/anti-fibrotic was used in conjunction with the needling procedure. IOP lowering medications (oral) will be described at baseline and post-implantation in the Effectiveness Population by class of medication (carbonic anhydrase inhibitors or alpha-agonist hypotensive agent). Visual field exam will be summarised descriptively at baseline and for all time points of interest (as described in Section 4.1) in the Safety Population. All BCVA values will be converted to logarithm of the minimum angle of resolution (logMAR) units.³ To do this, Snellen values will be converted by taking the negative base 10 logarithm of the decimal. ETDRS letters will be converted to approximate Snellen scores by the following formula.

$$\text{Snellen} \cong \exp \left\{ \frac{1}{50} (\text{ETDRS} - 85) \right\}.$$

This will then be converted into logMAR units using the negative base 10 logarithm of the decimal as above. Any non-numerical BCVA values (i.e. including count fingers, hand movement, light perception and non-light perception) will also be converted to logMAR units as described below:⁴

Non-numerical BCVA value	LogMAR
Count fingers (CF)	1.8
Hand movement (HM)	2.3

Light perception (LP)	2.8
No light perception (NLP)	3.0

4.4. Change in IOP and number of topical IOP-lowering medications after XEN 45 gel stent implantation

Change in IOP from medicated baseline and change in the number of topical IOP-lowering medications will be summarised. Change in number of IOP-lowering medications will be made by examining the class of the medication as follows:

- Beta Blocking Agents
- Carbonic Anhydrase Inhibitors
- Parasympathomimetics
- Prostaglandin Analogues
- Sympathomimetics In Glaucoma Therapy

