These will be compared to baseline and will be summarised descriptively at months 12, 24, 36 and 48 after XEN 45 Gel Stent implantation in eyes from the Effectiveness Population. Analyses will only include those with available data at each of the time points of interest and those who were not treated with Diamox on the day when decision was taken to implant XEN 45 Gel Stent.

A paired t-test will be applied for statistical analysis in comparing the difference between post baseline to baseline values. The assumptions of the test are as follows:

- No significant outliers in the differences between time points (which can be tested by a scatter plot of the data)
- The distribution of the differences in the dependent variable between the two time points should approximately follow a normal distribution (which can be tested through the Shapiro-Wilk test)
- The dependent variable is measured on a continuous scale

If the assumptions of the t-test are heavily violated then the non-parametric analogue (Wilcoxon Signed-Rank test) should be used to test the difference between time points.

4.4.1. Success over the long term of following implantation of the XEN 45 Gel Stent

Number and proportion of eyes achieving a 20% reduction in IOP from medicated baseline, and number and proportion of eyes with an IOP between 6 and 18 mmHg, IOP between 6 and 17 mmHg, ..., down to IOP between 6 and 12 mmHg will be described by the time-windows described in Section 4.1 in eyes from the Effectiveness Population that did not undergo SSI for glaucoma, and were not treated with Diamox on the day when decision was taken to implant XEN 45 Gel Stent.

The number and proportion of eyes achieving qualified or complete success at each time point of interest (i.e. 12, 24, 36, 48 and >51 months) after XEN 45 Gel Stent implantation will be summarised descriptively. Analyses will be conducted in the Effectiveness Population.

The time from XEN 45 Gel Stent implantation to SSI for glaucoma will be described using Kaplan Meier curves.

4.5. Safety over the long term following implantation of the XEN 45 Gel Stent

Surgical complications and post-operative AESIs will be summarised descriptively using frequencies and percentages.

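### Success is counted regardless of bleb needling, and no planned output shows how many successes, or Month 36/48 values, followed a needling

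*SAP*

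**What the plan says.** The Protocol (Synopsis and 6.2) and SAP 1.4 define success in the same way. Complete success is a 20% or greater "reduction from medicated baseline with no SSI for glaucoma and no clinical hypotony while taking no topical IOP-lowering medications". Qualified success keeps the IOP and SSI conditions and requires no "clinical hypotony while staying on the same number or fewer topical IOP-lowering medications than at baseline". Needling appears in neither definition.

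Needling is a data item of its own. Protocol 10.7 states: "Date of needling procedures performed on the bleb after XEN 45 Gel Stent implantation will be collected throughout the study period". It has its own row, apart from SSI, in Protocol Table 2 and in the SAP 1.8 schedule. Protocol 10.8 deals with SSI separately: "SSIs for glaucoma include but are not limited to trabeculectomy, table shunt, second gel stent, i-Stent, GATT, ABiC, and transscleral cycloablative procedures".

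The planned use of needling data is descriptive. Protocol 14.2.3 says: "Ocular medical history, IOP lowering medications and needling procedures will be summarized descriptively". SAP 4.3 says: "Needling procedures will be summarized in the Safety Population by the time windows indicated in Section 4.1". It also matches needling dates with anti-metabolite or anti-fibrotic dates, to describe use of those agents during needling.

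For effectiveness, SAP 4.4.1 reports "The number and proportion of eyes achieving qualified or complete success at each time point of interest" in the Effectiveness Population, and SAP 4.4 summarises IOP and medication change at Months 12, 24, 36 and 48. Neither section mentions needling. Under SAP 4.1 the value used for a time point is that of the latest visit in its window (Months 33 to 39 for Month 36), with no rule about a recent needling.

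**The concern.** The objective is the long-term performance of the stent. An eye off all drops after several needlings and an eye that needed no further procedure are both scored as complete successes. The reported proportion therefore describes the stent together with whatever needling followed. Similarly, an IOP reading taken soon after a needling can be the Month 36 value, because the latest visit in the window is taken.

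A reader of the final report will want to know how much of the success rate was reached without needling. The plan collects what is needed to answer this but schedules no analysis that does. An answer produced after the data are seen would be post hoc.

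**Working it through.** **Is needling already excluded as an SSI?** The list in Protocol 10.8 does not name needling, but it is open-ended. Two features settle the likely intent. Needling is collected separately. Extraction also ends at the last visit or the "date on which the patient had a SSI for glaucoma, whichever occurs first" (SAP 1.6), while SAP 4.1 tabulates needlings to beyond 48 months with no such stop. The documents therefore do not treat needling as an SSI, although they never say so.

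**Can the planned tables be combined to give needling-free success?** Three obstacles:

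1. *Windows.* Month 36 values come from Months 33 to 39, which straddle the needling windows > 24 to ≤ 36 and > 36 to ≤ 48 months. Month 48 values (Months 45 to 51) straddle > 36 to ≤ 48 and > 48. The needling windows also jump from < 3 to > 6 months, so needlings between 3 and 6 months fall in none.
2. *Restrictions.* The IOP-change analysis needs data at the time point and no Diamox at baseline. The IOP-threshold analysis in 4.4.1 drops eyes with SSI and eyes on Diamox at baseline. The needling count has none of these restrictions.
3. *Margins.* Even with identical eyes and windows, two separate counts only bound the overlap. Assume 60 eyes, 30 successes (50%) and needling in 20% of eyes (12). Needled successes lie between max(0, 30 + 12 − 60) = 0 and min(30, 12) = 12. Needling-free success is then anywhere from 18/60 = 30% to 30/60 = 50%. With needling in 40% of eyes (24), it lies between 6/60 = 10% and 50%.

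**The plan's own figure.** The only sizing figure is the precision of the mean IOP change (Protocol 14.1, SAP 2): mean −5.6, SD 6.32, n = 60. The half-length is 1.960 × 6.32/√60 = 1.60, giving −7.20 to −4.00 mmHg, which reproduces the stated interval. It does not bear on success, for which no rate or precision is given.

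**Illustration of size.** Let S be the success rate as defined and f the share of successes with a needling before the visit used. Then

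needling-free success = S × (1 − f).

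S and f are both assumed. Counts are out of an assumed 60 eyes, rounded to whole eyes:

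| S | f = 0 | f = 20% | f = 40% |
|---|---|---|---|
| 30% | 18 (30%) | 14 (23%) | 11 (18%) |
| 50% | 30 (50%) | 24 (40%) | 18 (30%) |
| 65% | 39 (65%) | 31 (52%) | 23 (38%) |

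For the middle row the Wilson 95% intervals are 38–62%, 29–53% and 20–43%. If f = 0, nothing changes.

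**The case against.** The strongest reply is that this is a choice of estimand. The definitions are the same wherever they appear, and the stated aim is to describe stent surgery in ordinary European practice. Success regardless of needling is a coherent target for that aim. This stands, and the definitions need not change. A reader might infer that the success definition is faulty or that the planned rates are wrong; the documents do not support that.

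It can also be said that needling is not ignored. Its dates feed a count by window and the description of anti-metabolite use, and late needling will be visible in the 24-to-36 and 36-to-48-month rows. This is true, but none of these outputs says which eyes were successes.

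A reader might further infer that the needling count and the effectiveness results come from unrelated populations and cannot be linked. That goes too far. SAP 4 has every effectiveness table also show all included eyes, which largely overlap the Safety Population, and at eye level the link is simple. Only the planned aggregate tables cannot be cross-classified.

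Finally, one could try to project a success rate. With the change Normal(−5.6, 6.32) and an assumed baseline of 21 mmHg, P(change ≤ −4.2) = Φ(1.4/6.32) ≈ 59%. This covers only the IOP criterion, leaving out SSI, clinical hypotony and the medication limit. It also moves with the assumed baseline: about 62% at 18 mmHg and 54% at 25 mmHg. It should not be used as a success rate from which to subtract needled eyes.

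**Conclusion.** The point holds as a gap in planned reporting on a secondary, descriptive outcome, and on the Month 36 and Month 48 values of the main IOP analysis. As the SAP stands, the report cannot say what proportion of eyes succeeded without needling, nor how many of the values analysed followed one.

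The size is unknown. It depends entirely on f: each 10% of successes with a prior needling lowers needling-free success by 10% in relative terms, or 5 points if S = 50%. A reader might also infer that readings just after a needling drive the Month 36 result. The window rule permits such readings, but nothing in the documents indicates how often they occur.

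The conclusion rests on reading needling as distinct from SSI, which the separate collection and the stop of extraction at SSI support.

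**What to change.** Keep both success definitions and amend the SAP as follows.

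- **SAP 1.4:** state that success is counted regardless of needling and that needling is not an SSI. Say also how the conjunctival bleb revision mentioned in SAP 4.3 is classified.
- **SAP 4.4.1:** beside each qualified and complete success proportion, give a second figure on the same denominator: success with no needling between implantation and the visit used.
- **SAP 4.4:** for Months 36 and 48, give the number of eyes needled at any time before the visit used, and the number needled within 3 months before it. Fix in advance how a needling on the day of the visit, or with an unknown date, is counted.
- **Any IOP change by needling status:** label it descriptive only. Needling is a post-implantation event, so the contrast is confounded by indication.
- **SAP 4.1:** close the gap in the needling windows between 3 and 6 months.

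The cost is SAP wording and a few table rows; the needling dates are already collected. The downsides are small cells, since tables are already split by procedure, and a second success figure that can only be equal to or lower than the first.
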